### 8.4. Efficacy Analysis

All efficacy analyses will be performed on the FAS population. Also, analysis of the primary and secondary efficacy variables will be carried out on the Per Protocol population to assess the robustness of the findings. Safety outcomes will be analyzed on the Safety population.

CONFIDENTIAL

Confidential	MyRisk	Date: 05 February 2024
	Protocol	
	PROTOCOL NUMBER: IBA1160	Version: 5.1

The primary efficacy endpoint “Proportion of complete responses over three cycles of chemotherapy after the start of the MEC administration” will be analyzed by means of a generalized linear model (GLIM) with logit link function, binomial distribution, and with “study treatment” (NEPA + Dex or Standard of care), “carboplatin use” (yes or no) and “country” as factors. Moreover, the GLIM model will be parameterized with generalized estimating equations with an exchangeable working correlation matrix to take into account clustered data (i.e. three repeated measures corresponding to as many cycles of chemotherapy within each subject). Results will be reported as odds ratios with associated two-sided 95% confidence intervals and p-values.

The same statistical approach will be used for all the secondary efficacy endpoints except for the following outcomes “delay and/or dose reduction” which will be analyzed using a Stratified Wilcoxon Rank Sum test blocking for carboplatin use and country.

Missing data on the primary efficacy endpoint will be imputed using conventional Multiple Imputations approach. The SAS® MI procedure will be employed to perform multiple imputation in order to obtain Maximum Likelihood estimates which, by definition, are unbiased under a MCAR and MAR mechanism for missing values. Details on Multiple Imputations will be provided with the SAP.

Missing data on secondary efficacy endpoints will be imputed using last observation carried forward (LOCF). The overall type I family-wise error rate for testing the primary and the secondary efficacy parameters is controlled at the 0.05 significance level without the need for adjustments since the study is planned with a single primary endpoint and since secondary endpoints are only supportive of primary endpoint findings. All statistical analyses will be performed using SAS version 9.4 or later.

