9.2. Determination of Sample Size

A sample of 410 randomised subjects, each scheduled to be measured 3 times/cycles, achieve a 80% power when using a two-sided Wald test from a GEE analysis to test whether the proportion of Complete response expected in the Test group (71%) differs from that expected in the Control group (60%) at a significance level of 0,050. The subjects are randomly split between a Test group and a Control group, with 50% of the subjects assigned to the Test group. The measurements of each subject will be made at the following times/cycles expressed as proportions of the total study time: {0%; 50%; 100%}. Missing values are assumed to occur completely at random (MCAR) or at random (MAR). These missing value proportions will be combined to form the pairwise observant probabilities using the Independent method. The anticipated proportions missing at each measurement time/cycle are {0%; 7.5%; 15%}. Based on these attrition rate scenario, a sample of 348 completer subjects is expected. The correlation between observations on the same subject is assumed to be 0.5 (ballpark estimate). All computations are performed using PASS 14 software.

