9.4.1. Imputation of endpoints data

To achieve the largest possible sample, imputation techniques will be used to impute missing data for the FAS population. Missing data on the primary efficacy endpoint will be imputed using conventional Multiple Imputations approach. The SAS® MI procedure will be employed to perform multiple imputation in order to obtain Maximum Likelihood estimates which, by definition, are unbiased under a MCAR and MAR mechanism for missing values.

The following MI procedure code will be used to perform MI with 5 imputations.

```
PROC MI data = dataset seed=s out = MIdataset n impute = 5;
VAR study_treatment carboplatin country vis1_event - vis3_event;
CLASS study_treatment carboplatin country vis1_event - vis3_event;
monotone logistic;
RUN;
```

The exact names of the variables may differ.

9.4.2. Missing data within the FAS population on secondary efficacy endpoints will be imputed using the last observation carried forward (LOCF). Primary Efficacy Endpoint

The primary efficacy endpoint “Proportion of complete responses over three cycles of chemotherapy after the start of the MEC administration” will be analyzed by means of a generalized linear model (GLIM) with logit link function, binomial distribution and with “study treatment” (NEPA + Dex or Standard of care), “carboplatin use” (yes or no) and “country” as factors, using data from the overall period of three cycles.

Moreover, the GLIM model will be parameterized with generalized estimating equations with an exchangeable working correlation matrix to take into account clustered data (i.e. three repeated measures corresponding to as many cycles of chemotherapy within each subject). Results will be reported as odds ratios with associated two-sided 95% confidence intervals and p-values.

The results will be obtained via the GENMOD procedure, using following code:

```
PROC GENMOD data = dataset;
CLASS id study_treatment carboplatin country;
MODEL complete_response = study_treatment carboplatin country / dist = bin
link = logit;
REPEATED subject = id / type = exch covb corrw;
LSMEANS study_treatment / diff exp ilink cl;
RUN;
```

The exact names of the variables may differ.

With MI the code will be modified to:

```
PROC GENMOD data = dataset;
CLASS id study_treatment carboplatin country;
MODEL complete_response = study_treatment carboplatin country / dist = bin
link = logit;
REPEATED subject = id / type = exch ecovb;
LSMEANS study_treatment / diff exp ilink cl;

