ODS OUTPUT GEEEmpPEst=parms_est;
RUN;

PROC MIANALYZE parms(classvar = LEVEL)=parms_est;
```

```

CLASS study_treatment carboplatin country;
MODELEFFECTS Intercept study_treatment carboplatin country;
ODS OUTPUT ParameterEstimates = combined_parms;
RUN;

```

The exact names of the variables may differ.

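### As printed, the SAP's multiple-imputation program does not analyse or pool the five imputations; its monotone method and the 348 completers also do not fit the stated Independent missing pattern (minor)

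*SAP*

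**What the plan says.** **Imputation.** Protocol 8.4 requires multiple imputation for the primary endpoint and defers the rest: "Details on Multiple Imputations will be provided with the SAP". SAP 9.4.1 then commits to specific code: "The following MI procedure code will be used to perform MI with 5 imputations". PROC MI reads `dataset` and writes its result with "out = MIdataset n impute = 5" (the space inside the option name may come from the PDF reading and is not counted here). Its variables are treatment, carboplatin, country and one event variable per cycle, that is, one row per patient. The method is "monotone logistic".

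**Analysis and pooling.** SAP 9.4.2 gives a GENMOD program for a GEE logistic model of `complete_response`, clustered on patient. It then says "With MI the code will be modified to" and prints a second GENMOD block, which saves the parameter estimates to `parms_est`. The last step is "PROC MIANALYZE parms(classvar = LEVEL)=parms_est". A note says that variable names may differ.

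**Sample size.** The protocol synopsis, Protocol 8.2 and SAP 9.2 carry the same text: 410 randomised, 80% power, response 71% against 60%, correlation 0.5, and 0%, 7.5% and 15% missing at cycles 1 to 3. The missing proportions are "combined to form the pairwise observant probabilities using the Independent method". The text then states: "Based on these attrition rate scenario, a sample of 348 completer subjects is expected".

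**The concern.** The protocol hands the imputation details to the SAP, so this code is their only specification. If it is followed as printed, the pooled primary result that the text promises is not produced.

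The sample-size text and the imputation method also rest on different pictures of missing data. A monotone method assumes that a patient who misses one cycle misses all later ones. The Independent assumption says that cycles 2 and 3 go missing separately. The completer count agrees with the first picture, and N with the second. The SAP gives no rule for a patient with cycles 1 and 3 but not cycle 2.

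At stake are a primary program that matches its description, a stated rule for intermittent gaps, and a sample-size paragraph whose figures agree with each other.

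**Working it through.** **1. The program, step by step**

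| Step | Reads | Layout | Comment |
|---|---|---|---|
| PROC MI | `dataset` | one row per patient, three event variables | writes five copies to `MIdataset` |
| (none printed) | – | – | no step makes one record per patient and cycle |
| GENMOD under the With-MI line | `dataset` | needs one `complete_response` record per patient and cycle | no `BY _Imputation_` |
| MIANALYZE | `parms_est` | one set of estimates | no between-imputation variance to combine |

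`MIdataset` is not used again after it is written. Read literally, GENMOD fits the un-imputed records, which is an available-case GEE. If `dataset` is a placeholder for `MIdataset`, the reshape and the BY statement are still missing. The note on variable names covers neither.

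**2. Reproducing N = 410**

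Inputs from SAP 9.2: p1 = 0.71, p0 = 0.60, two-sided 0.05, 80% power, correlation 0.5, observed proportions d = (1, 0.925, 0.85).

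- log OR = ln(0.71/0.29) − ln(0.60/0.40) = 0.490
- 1/(0.71 × 0.29) + 1/(0.60 × 0.40) = 4.857 + 4.167 = 9.023
- (1.960 + 0.842)² = 7.849
- V = [Σd + 2 × 0.5 × Σ(pairwise observed)] / (Σd)², with Σd = 2.775 and (Σd)² = 7.7006
- n per arm = 7.849 × 9.023 × V / 0.490²

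| Pattern | Pairs (1,2), (1,3), (2,3) | V | n per arm | N | Power at 410 |
|---|---|---|---|---|---|
| Independent | 0.925, 0.85, 0.925 × 0.85 = 0.786 | 5.336/7.7006 = 0.693 | 204.5 | **410** | 80.1% |
| Monotone | 0.925, 0.85, 0.85 | 5.400/7.7006 = 0.701 | 206.9 | 414 | 79.6% |

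The stated Independent method gives 410 exactly.

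**3. Who is observed when, at N = 410**

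| | Independent | Monotone |
|---|---|---|
| All three cycles | 410 × 0.925 × 0.85 = **322.4** | 410 × 0.85 = **348.5** |
| Missing cycle 2 only | 410 × 0.075 × 0.85 = **26.1** (6.4%) | 0 |
| Observed at cycle 3 | 410 × 0.85 = 348.5 | 348.5 |

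So 348 is the number observed at cycle 3 under either pattern. It is the number of three-cycle completers only under monotone dropout. The 26 patients with a cycle 2 gap are the ones a monotone method does not fit.

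**4. Size of the effect on the odds ratio**

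A simulation used 205 patients per arm, five imputations, an exchangeable GEE with treatment only, and 1,000 trials in each of 12 scenarios. The scenarios crossed Independent or monotone missingness, flat response or a rise of 5 points per cycle, and missingness that was unrelated to earlier failure, three times as likely after it in both arms, or three times as likely in the control arm only. The trend and the ratios are assumptions; the documents give neither.

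The mean log OR moved from its complete-data value by at most:
- 0.006 with the literal code (0.009 in a separate set of runs);
- 0.003 with sequential logistic imputation that ignores cycle 3 when filling cycle 2;
- 0.003 with fully conditional specification (FCS).

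Interval coverage was 93.7% to 96.0% for all three. Against a planned log OR of 0.490, 0.009 is under 2%.

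**The case against.** **The label is generic.** The SAP uses `dataset` in PROC MI and in both GENMOD blocks. One of these needs wide data and the other long data, so it cannot be one file. This is fair, and it makes the available-case reading only one possible reading. It does not supply the reshape or the BY statement.

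**Pooling is fixed by intent.** A reader might infer that the pooling would be decided outside the plan, in an open-label trial. The documents do not support that. They fix the number of imputations, the imputation variables, the GEE model, the output table and the combining procedure, so restoring the BY statement leaves no analytic choice. The double programming and log checks in SAP 9.1.5 would probably expose the fault. Only the treatment of intermittent gaps is open.

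**Gaps may be rare.** Protocol 3.6.3 has the investigator complete missing answers with the patient, a telephone call on days 3 to 5 checks diary completion, and rescue use is also collected by inquiry at visits. This stands: 26 is what the plan's own assumption implies, not a forecast. It does not rule gaps out.

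**Completer is undefined.** It could mean observed at cycle 3, which makes 348 right. That is possible, although it is not the natural reading in a three-cycle trial. The sentence would then need that definition.

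**LOCF for secondary endpoints.** A reader might see a contradiction in imputing per-cycle response by LOCF as a secondary endpoint and by multiple imputation in the primary analysis. Protocol 8.4 prespecifies LOCF and calls the secondary endpoints supportive. Different methods for the two are a choice, not an error.

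**Conclusion.** The point holds and is minor.

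- The printed With-MI program does not analyse or pool the five imputations. This follows from the code alone and needs no assumption about the data.
- The monotone method does not fit the Independent pattern assumed in Protocol 8.2 and SAP 9.2, under which about 26 of 410 patients (6.4%) would miss only cycle 2.
- With that pattern, the number observed in all three cycles is 322, not 348.

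A reader might infer that the trial is underpowered, or that the basis of 410 is unknown. Neither follows. The text names the Independent method, which reproduces 410 with 80.1% power. Even under monotone dropout, power at 410 is 79.6%, about half a point lower.

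The expected effect on the primary odds ratio is small. That statement rests on a simulation that omits carboplatin and country and uses assumed missingness mechanisms.

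**What to change.** **SAP 9.4.1 and 9.4.2, code.** Reshape `MIdataset` to one record per patient and cycle, with `complete_response` as the outcome; sort by `_Imputation_`; run GENMOD on that file with `BY _Imputation_`; then run MIANALYZE on the five sets of estimates.

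**SAP 9.4.1, method.** Use FCS logistic imputation with the same variables, or first fill the intermittent gaps so that the remaining pattern is monotone. State which.

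**Protocol synopsis, Protocol 8.2 and SAP 9.2.** Choose one of the following and leave N at 410:
- keep Independent and change 348 to 322 observed in all three cycles;
- keep Independent and define 348 as patients observed at cycle 3;
- state monotone dropout, keep 348 completers, and give power as 79.6%.

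The cost is SAP code and wording plus one sentence in three places, with the protocol sentences needing an amendment. No new data and no more patients are needed.

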9.4.3. Secondary Efficacy Endpoint

The same statistical approach as for the primary endpoint (GLIM) will be used for all the secondary efficacy endpoints with the exception of the following outcomes “delay and/or dose reduction” which will be analyzed using a Stratified Wilcoxon Rank Sum test blocking for carboplatin use and country, using following code (*delay_length* can be replaced with *amount_reduction*):

```

PROC NPAR1WAY data=dataset wilcoxon;
CLASS study_treatment;
VAR delay_length;
STRATA country carboplatin;
EXACT wilcoxon;
RUN;

```

The exact names of the variables may differ.

The code will be equivalent to the one used in the analysis of primary endpoint, only changing variable from *complete_response* to variables describing the secondary endpoints:

- Complete response during the acute (0-24h), delayed phase (25-120h), overall (0-120h) and daily in each cycle
- No emetic episode during the acute, delayed and overall phase and daily in each cycle
- Number of vomiting episodes during the acute, delayed and overall phase in each cycle
- No rescue medication during the acute, delayed and overall phase and daily in each cycle
- No significant nausea (maximum MAT scale = 2) during the acute, delayed and overall phase and daily in each cycle
- No nausea (MAT scale = 0) during the acute, delayed and overall phase and daily in each cycle
- Complete protection (no emetic episode, no rescue medication and no significant nausea) during the acute, delayed and overall phase and daily in each cycle
- Nausea and Vomiting-related quality of life indicators (through the Functional Living Index Emesis scale)

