### 3.5. Study Endpoints

Definition of the assessment of time-related study efficacy endpoints:

Time-related efficacy study endpoints assessment will start at time 0 defined as the start time of the chemotherapy administration on Day 1 of each of the three cycles.

CINV indicators, such as nausea and vomiting, their intensity and frequency and Quality of Life will be evaluated during the acute phase of emesis, from 0 to 24 hours from the start of chemotherapy, in the delayed phase of emesis, from 24 to 120 hours from the start of chemotherapy, and overall during each day (i.e., day 1, 2, 3, 4 and 5) from the start of chemotherapy.

The primary endpoint will be the proportion of complete responses (no emetic episode and no rescue medication), during the overall phase (0-120h), after the start of the MEC administration over three cycles of chemotherapy.

Clinical secondary endpoints will be evaluated during each cycle:

- Complete response during the acute (0-24h), delayed phase (>24-120h), overall (0-120h) and daily in each cycle;
- No emetic episode during the acute, delayed and overall phase and daily in each cycle;
- Number of vomiting episodes during the acute, delayed and overall phase and daily in each cycle;
- No rescue medication during the acute, delayed and overall phase and daily in each cycle;
- No significant nausea (maximum MAT scale = 2) during the acute, delayed and overall phase and daily in each cycle;
- No nausea (MAT scale = 0) during the acute, delayed and overall phase and daily in each cycle;
- Complete protection (no emetic episode, no rescue medication and no significant nausea) during the acute, delayed and overall phase and daily in each cycle
- Nausea and Vomiting-related quality of life indicators (through the Functional Living Index Emesis scale)
- Collection of chemotherapy delays and/or dose reductions (Delay of chemotherapy administration due to CINV will be also evaluated as part of health economic endpoints, see below)

Health economic endpoints will be evaluated during the study cycles:

- Number of days and daily doses of rescue medication administered for the treatment of CINV
- Number of re-hydration bags given for at least grade 2 vomitings (CTCAE v5)
- The number of days of unplanned hospitalisations related to CINV and department of hospitalization (type of ward)
- The number of outpatient physician visits and health care consultations due to CINV (e.g., general practitioner)

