There are no changes from the Study protocol v5.1 (version from the 05-FEB-2024).

3. Activities to Be Done before Execution of Final Analyses

- The following tasks have to be done before final execution of analysis: Study database have to be locked (Status "read only"). All relevant data-management processes are finalized (approval by Project data manager or Project Manager).
- Disposition of patients in analysis sets and list of protocol deviations have to be approved.
- Assignment of adverse events to study treatment has to be approved.
- Coding of Adverse events and medical history have to be finalized and approved.
- A reconciliation of serious adverse events (SAEs), i.e. a comparison of SAEs in the clinical database and SAEs reported to the sponsor must be performed.
- Data from the Patient's diary, MAT questionnaire and FLIE questionnaire have to be digitalized, included in the clinical database and checked for discrepancies.

4. Study Objectives

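### SAP 9.4.3 carries the primary binomial-logit GEE over to two secondary endpoints that are not yes/no (vomiting episode counts and FLIE scores), and the available text names no valid model for them

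*SAP*

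**What the plan says.** The primary model is set out in SAP 9.4.2 (Primary Efficacy Endpoint). The code line reads "MODEL complete_response = study_treatment carboplatin country / dist = bin", followed by a logit link and an exchangeable working correlation over the three cycles. On reporting, the SAP states: "Results will be reported as odds ratios with associated two-sided 95% confidence intervals and p-values".

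SAP 9.4.3 extends this to the secondary endpoints. It keeps the same GLIM approach for all of them apart from delay and dose reduction, which get a stratified Wilcoxon test, and adds: "The code will be equivalent to the one used in the analysis of primary endpoint, only changing variable from" complete response to the variables in a list of eight endpoints. Two entries in that list are:

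- "Number of vomiting episodes during the acute, delayed and overall phase in each cycle"
- "Nausea and Vomiting-related quality of life indicators (through the Functional Living Index Emesis scale"

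Protocol 8.4 sets the same rule with the same single exception: "The same statistical approach will be used for all the secondary efficacy endpoints except for the following outcomes" delay and/or dose reduction.

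Protocol 3.5 words the vomiting endpoint differently, as "Number of vomiting episodes during the acute, delayed and overall phase and daily in each cycle". SAP Section 2 nevertheless declares: "There are no changes from the Study protocol v5.1".

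**The concern.** A binomial model with a logit link describes the probability of an event, and its treatment effect is a ratio of odds. The number of vomiting episodes and a FLIE score are not events, so there are no odds to compare unless the plan says what counts as a response. It does not.

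The authors evidently saw that not every secondary endpoint fits the primary model, because they exempted delay and dose reduction. The same reasoning was not applied to the count and the score.

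Vomiting frequency and quality of life are both named among the CINV indicators in the secondary objectives (SAP 4.2). If the written code cannot be used for them, the distribution, link and effect measure must be chosen outside the plan. The trial is open label, and SAP 9.9 allows country summaries of endpoint events by arm before the final analysis. A model chosen late could therefore be chosen after by-arm results have been seen.

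**Working it through.** **1. The plan's own figure for this model.** The only stated number tied to the binomial-logit GEE is the sample size (SAP 9.2). Inputs: complete response 71% and 60%, two-sided alpha 0.05, power 80%, 1:1 allocation, correlation 0.5, proportions missing 0, 7.5% and 15%, combined independently.

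- Variance factor v = Σ(π_jk ρ_jk)/(Σπ_j)², with observed proportions 1, 0.925 and 0.85.
- Numerator: 2.775 + 2 × 0.5 × (0.925 + 0.85 + 0.925 × 0.85) = 2.775 + 2.561 = 5.336. Denominator: 2.775² = 7.701. So v = 0.693.
- n per arm = (1.960 + 0.842)² × [1/(0.71 × 0.29) + 1/(0.60 × 0.40)] × v / (logit 0.71 − logit 0.60)² = 7.849 × 9.023 × 0.693 / 0.490² ≈ 204.5, rounded up to 205.
- Total 410, as stated.

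The model is coherent for the yes/no primary endpoint, and nothing below changes N.

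**2. The eight endpoints in SAP 9.4.3, by type.**

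| Endpoint | Type | Suits binomial-logit? |
|---|---|---|
| Complete response | yes/no | yes |
| No emetic episode | yes/no | yes |
| Number of vomiting episodes | count | no |
| No rescue medication | yes/no | yes |
| No significant nausea | yes/no | yes |
| No nausea | yes/no | yes |
| Complete protection | yes/no | yes |
| FLIE quality of life | summed score | no |

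The count type follows from the MAT and the diary, where the patient writes in how many times vomiting happened. The score type follows from SAP 7.9, which sums 18 items into a total made up of a nausea and a vomiting domain.

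**3. What the model requires.** The fitted mean μ enters as log[μ/(1 − μ)] and the variance as μ(1 − μ), so μ must lie between 0 and 1. Nothing confines the mean of an episode count or a FLIE sum to that range. The code gives a single response variable and no number of trials, so neither outcome can be read as a proportion. Even where a routine returned a number, exp(β) would not be an odds ratio for any event that the plan defines.

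**4. Could a cut-off be implied?** Splitting vomiting at zero gives the separate no-emetic-episode endpoint, already on the list. No responder cut-off for FLIE appears anywhere in the available text.

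**5. Does other text supply a model?**

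- SAP 10.1: the primary figure and the figures for all six yes/no endpoints are titled logistic regression. Figure 14.2-4 (vomiting episodes) says only regression, and Figure 14.2-9 (FLIE) names no method. This disagrees with 9.4.3 but states no distribution, link or effect measure.
- SAP 9.1.4: quantitative endpoint variables are checked by histogram and Shapiro-Wilk test. No model choice is tied to the result.
- SAP Section 11 refers layouts to Appendix 1, which was not available.

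**6. Daily counts.** Protocol 3.5 and Figure 14.2-4 include daily vomiting counts. SAP 6.2 and 9.4.3 do not.

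**7. Illustration.** One simulated data set of each kind, 410 subjects × 3 cycles, was fitted in Python with treatment as the only factor and exchangeable correlation. The counts (range 0 to 12) were generated with a rate ratio of 0.7. The FLIE-type scores (about 29 to 126) were generated with a mean difference of 5 before truncation at the scale limits. Both scales are assumed.

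| Outcome | Binomial-logit GEE | Alternative GEE |
|---|---|---|
| Count | no estimate | Poisson, log link: β = −0.395 (SE 0.154), rate ratio exp(−0.395) = 0.67 |
| FLIE-type score | no estimate | normal, identity link: difference 4.53 (SE 1.53) |

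This shows that the alternatives run on such data. It is not a prediction of what the SAS code would do.

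**The case against.** The best defence is that SAP 9.4.3 speaks of the GLIM approach, which the abbreviation list expands to a general class of models. On that view the figure titles, which drop the word logistic only for these two endpoints, and the distribution check in 9.1.4 show that the authors meant a suitable member of the class. Appendix 1 might settle the matter. That the plan is internally inconsistent, and does not deliberately choose logistic regression for a count, is a fair reading. But it still leaves both endpoints without a distribution, link or effect measure, and it conflicts with the instruction to change only the variable.

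It is also true that the endpoints are declared supportive (SAP 9.4), that Tables 14.2-4 and 14.2-9 will describe them whatever model is used, and that double programming and log checks (SAP 9.1.5) should catch a failed fit. Those points limit the damage and they stand. Quality checks do not, however, pre-specify the replacement model.

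A reader might infer that the SAS code would certainly fail, or would report an odds ratio distorted by a calculable amount. The documents support neither. SAS was not run, the illustration omits carboplatin use and country, and the outcome depends on how the software treats such a response and on episode frequencies that the documents do not give.

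**Conclusion.** The point holds on the text. The rule in SAP 9.4.3, backed by protocol 8.4, assigns a binomial-logit model and an odds ratio to 2 of 8 listed secondary endpoints for which they are not valid, and nothing available replaces them. This is an error in the stated rule, not just missing detail, and it should be fixed.

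Its size is 2 endpoints out of 8, for inference only. A count of affected treatment comparisons is tempting but not supported: the SAP does not say whether each cycle is tested separately, and SAP 7.9 says only that the FLIE domain scores will be presented. Nor do the documents support extending the criticism to the primary analysis, the sample size, the six yes/no endpoints or the descriptive tables.

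The conclusion assumes that Appendix 1 does not already name a model. If it does, what remains is a contradiction with 9.4.3 to be removed. The daily-count mismatch is a small separate inconsistency, best settled in the same edit.

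**What to change.** Before database lock, replace the code-substitution sentence in SAP 9.4.3 with text along these lines:

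> The binomial-logit code applies to the yes/no endpoints only. Number of vomiting episodes: GEE with log link and Poisson variance, robust standard errors, reported as a rate ratio with 95% CI. FLIE total, nausea and vomiting domain scores: GEE with normal distribution and identity link, reported as a mean difference with 95% CI. Both models use study treatment, carboplatin use and country as factors and an exchangeable working correlation over cycles.

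One model should be named per endpoint. A rank test or a responder cut-off would answer a different question and should not be left as an open alternative.

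In the same revision:

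- State whether daily vomiting counts are analysed, so that protocol 3.5, SAP 6.2, SAP 9.4.3 and Figure 14.2-4 agree.
- Record the departure from protocol 8.4 in SAP Section 2. Whether the protocol also needs amending is for the sponsor to decide.
- If Appendix 1 already names a model, cite it in 9.4.3 and make the two agree.

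The cost is a few lines of SAP text and code. No new data are needed, and N and the primary analysis do not change. The downside is that secondary results will carry three effect measures (odds ratio, rate ratio, mean difference), so they cannot be compared directly across endpoints.
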